### Variable list, sources, and data collection

The variables listed on the below data collection form will be incorporated into a secure REDCap database that research staff will use to enter the data. Patients will be assigned study ID numbers in the REDCap database. The REDCap database will contain identifying information, however, if de-identified data needs to be shared outside of the direct study team, the dataset can be downloaded without identifying variables such as MRN.

Variable Name	Role of Variable	Measurement Scale
Study ID	Unique identifier	Continuous (001 – n)
MRN	Link to EMR	String
Full name	Link to EMR	String
Date of ED presentation	Link to EMR	DMY
Age	Descriptive	Continuous
Race	Descriptive	Categorical, as reported in Epic
Ethnicity	Descriptive	Categorical, as reported in Epic
Sex at birth	Descriptive	Categorical, as reported in Epic
End stage renal disease or hepatic disease	Inclusion/exclusion criteria	Binary
Vasopressor dose to treat hypotension at any point during admission	Inclusion/exclusion criteria	Binary
On insulin pump therapy at baseline (prior to ED)	Inclusion/exclusion criteria	Binary
On combination insulin products (i.e. Novolin® 70/30, Novolog® 70/30, Humalog® 75/25, etc.) at baseline	Inclusion/exclusion criteria	Binary
Presenting pH (prior to intervention)	Inclusion/exclusion criteria	Continuous

Time of first pH	Calculate time to resolution	Continuous
Time of short-acting insulin start	Calculate time to resolution	Continuous
Time of first pH > 7.3	Outcome Calculate time to resolution	Continuous
Presenting blood glucose in mg/dL	Inclusion/exclusion criteria	Continuous
Time of first blood glucose < 250 mg/dL	Outcome Calculate time to resolution	Continuous
Blood glucose > 180 mg/dL in the 24 hours after IV insulin infusion discontinuation	Outcome	Binary
Blood glucose < 70mg/dL $\geq$ 1 time at any point while on IV insulin therapy or in the 24 hours after IV insulin infusion discontinuation	Outcome Prevalence of AE (hypoglycemia)	Binary
Blood glucose < 70mg/dL at any point between glargine start and 24 hours after IV insulin infusion discontinuation (control group only)	Outcome Prevalence of AE that may be contributable to study intervention (hypoglycemia)	Binary
Mean blood glucose in 24 and 48 hours after IV insulin infusion discontinuation	Outcome	Continuous
Presenting anion gap	Inclusion/exclusion criteria	Continuous
Time of first anion gap	Calculate time to resolution	Continuous
Time of first anion gap < 12	Calculate time to resolution	Continuous
Presenting serum bicarbonate level in mEq/L	Inclusion/exclusion criteria	Continuous
Time of first serum bicarbonate < 15 mEq/L	Calculate time to resolution	Continuous
Presence of ketonuria or ketonemia on presentation	Inclusion/exclusion criteria	Binary
Presenting Beta-Hydroxybutyrate in mmol/L	Inclusion/exclusion criteria	Continuous

Type I or Type II Diabetes	Descriptive	Binary
Prior to admission history of current basal insulin usage	Treatment determination if in intervention arm	Binary
Home Insulin Dose	Treatment determination if in intervention arm	Continuous
Time of IV insulin infusion initiation	Ensure protocol compliance Start of outcome measure	Date/Time
Time of IV insulin infusion discontinuation	Outcome	Date/Time
Time of SC insulin glargine administration	Descriptive Ensure protocol compliance	Date/Time
Exact dose of SC insulin glargine administered	Descriptive Ensure protocol compliance	Date/Time
Weight in kg	Determine insulin glargine dose for study order	Continuous
Date/time of ICU admission	Calculate ICU LOS post-infusion for study outcome	Date/time
Date/time of ICU discharge (defined as time of service switch to progressive care or general medicine)	Calculate ICU LOS post-infusion for outcome	Date/time
Date/time of IV insulin infusion start	Calculate LOS post-infusion for study outcome	Date/time
Date/time of hospital discharge	Calculate LOS for study outcome	Date/time

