## Study aims

Primary Outcome:

- 1) Does early administration of insulin glargine result in a shorter ICU length of stay when compared to usual care for the treatment of diabetic ketoacidosis?

Hypothesis: Early administration of insulin glargine will result in shorter ICU length of stay when compared to usual care in patients with DKA.

Secondary Outcomes:

- 1) Does early administration of insulin glargine result in a shorter hospital length of stay (defined as time between start of insulin infusion and discharge from hospital) when compared to usual care for the treatment of diabetic ketoacidosis?

Hypothesis: Early administration of insulin glargine will result in shorter hospital length of stay when compared to usual care in patients with DKA.

- 2) Does early administration of insulin glargine result in a faster recovery from DKA (defined as blood glucose < 200 and two of: Anion Gap  $\leq$  12, Serum Bicarbonate  $\geq$  15 mEq/L, or pH > 7.3) when compared to usual care for the treatment of diabetic ketoacidosis?

Hypothesis: Early administration of insulin glargine will result in a faster recovery from DKA (defined as blood glucose <200 and two of: Anion Gap  $\leq$  12, Serum Bicarbonate  $\geq$  15 mEq/L, or pH > 7.3) when compared to usual care for the treatment of diabetic ketoacidosis.

- 3) Does early administration of insulin glargine result in a shorter duration of elevated anion gap (defined as time with anion gap > 12) when compared to usual care for the treatment of diabetic ketoacidosis?

Hypothesis: Early administration of insulin glargine will result in a shorter duration of elevated anion gap (defined as time with anion gap > 12) when compared to usual care for the treatment of diabetic ketoacidosis.

- 4) Does early administration of insulin glargine result in a shorter duration of time on IV insulin infusion when compared to usual care for the treatment of diabetic ketoacidosis?

Hypothesis: Early administration of insulin glargine will result in a shorter duration of time on IV insulin infusion when compared to usual care for the treatment of diabetic ketoacidosis.

- 5) Does early administration of insulin glargine result in a lower prevalence of rebound hyperglycemia, defined as blood glucose > 180 mg/dL in the 24 hours after IV insulin infusion discontinuation, when compared to usual care for the treatment of diabetic ketoacidosis?

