Lastly, Rappaport et al. (2019) conducted a single-center, retrospective cohort study of 106 admissions for DKA comparing early vs late initiation of basal insulin. Patients admitted to the MICU who were treated with home-dose basal insulin prior to DKA resolution and within 24 hours of IV insulin infusion initiation ( $n = 33$ ) were compared to patients who were initiated on basal insulin within 6 hours before or any time after IV insulin infusion discontinuation ( $n = 73$ ). Transition from IV insulin infusion to subcutaneous insulin was not addressed in a protocol and was left to the discretion of the provider. Patients were excluded if they had surgery within 48 hours of IV insulin infusion, were pregnant, were in vasopressor dependent shock, or had another indication for insulin therapy. Patients in the early group had initial daily doses of basal insulin of 0.48 U/kg (IQR: 0.34 – 0.62) compared to 0.44 U/kg in the late group. Patients in the early insulin group had their first dose of basal insulin 2.5 hours (IQR: 0.4 – 6.4) after IV insulin infusion initiation. There was no difference in transitional failure (early group: 6% vs late: 10%;  $p = 0.717$ ), rebound hyperglycemia (early: 81% vs late: 88%; OR: 0.59, CI: 0.16 – 2.25), hypoglycemia events (early: 33% vs late: 55%; OR: 0.41, CI: 0.16-1.05); time to anion gap closure: (early: 7.8h vs late: 9.1h;  $p = 0.73$ ), length of ICU stay (early: 34h vs late: 33.3h,  $p = 0.83$ ), or hospital length of stay (early: 2 days vs late: 2 days,  $p = 0.9$ ). There was a statistically significant decrease for time on IV insulin infusion (early: 13.8h vs late: 17.1h,  $p = 0.04$ ).

Preliminary research at Regions Hospital determined that in 40 randomly selected patients admitted for DKA in 2019, the mean dose of basal insulin initiated was 0.39 units per kilogram, and it was administered a mean of 22.4 hours after initiation of the IV insulin infusion and 1.86 hours prior before discontinuation of IV insulin, which is consistent with ADA recommendations

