### Statistical analysis plan

The primary outcome and secondary outcomes 1-4 and 7 will follow the same analysis plan to study the difference in the distribution of time to an endpoint. First, the distributions for each of these outcomes will be evaluated to determine if the distribution is normal or non-parametric. If the distribution is normal, that outcome will be analyzed using a two-tailed unpaired t-test. If the distribution is non-parametric, that outcome will be analyzed using a Wilcoxon rank sum test. We expect length of stay data to follow a non-parametric distribution. In secondary outcome 2, the outcome measured is the time at which all of the necessary criteria are hit for the first time simultaneously, which accounts for the transient nature of some of these measures.

Secondary outcomes 5-6 will measure the prevalence of each of these outcomes. Prevalence was chosen over incidence in order to account for multiple instances of rebound hyperglycemia or hypoglycemia occurring within the specified timeframe for each and also the amount of time it takes to clinically reverse these conditions. For both of these outcomes, a two-proportion z test will be run to find the difference in the amount of time each treatment arm cumulatively spent with the specified condition. Finally, for the outcomes relying on certain lab values, we will examine time from IV insulin infusion start to outcome labs in both groups. If there is significant variability between the experimental and SOC arms, we will adjust for this statistically. Group randomization should ensure that variability is

equally distributed between groups, however, there is a chance of bias (e.g., if the experimental group fares better and thus are slower to get nursing checks.)

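### Secondary outcome 3 is defined as time with anion gap above 12, but the planned form fields yield only time to the first value below 12

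*Combined protocol and SAP*

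**What the plan says.** Study aims, secondary outcome 3, asks whether early glargine gives a "shorter duration of elevated anion gap (defined as time with anion gap > 12"). Read as written, this is an amount of time.

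The table under Variable list, sources, and data collection has three anion gap items: "Presenting anion gap" (an eligibility item), "Time of first anion gap" and "Time of first anion gap < 12". The two times share one stated role, the calculation of time to resolution. The same section introduces the table by saying that "The variables listed on the below data collection form will be incorporated into a secure REDCap database". It lists no serial anion gap values, no reopening item and no time of last closure.

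The Statistical analysis plan treats outcome 3 as a time-to-endpoint quantity, in a sentence that begins "The primary outcome and secondary outcomes 1-4 and 7 will follow the same analysis plan to study the difference in the distribution of time to". The test is a t-test or a Wilcoxon rank sum test. Its one remark on values that come and go concerns secondary outcome 2, which is timed when "all of the necessary criteria are hit for the first time simultaneously, which accounts for the transient nature of some of these measures". It gives no corresponding rule for outcome 3.

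**The concern.** An outcome worded as time spent in a state needs the whole series of readings. Two time stamps give only the interval to a first crossing. If the form is followed literally, a patient whose gap closes and later reopens scores the same as one whose gap closes at the same hour and stays closed. No scoring formula is written, so this follows from the listed fields and the time-to-endpoint wording.

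The threshold differs as well. The definition stops counting at 12; the form waits for a value below 12. Secondary outcome 2 also uses 12 or less, so the form disagrees with both outcomes that rely on the anion gap.

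Reopening is not far-fetched in this setting. The Background gives prevention of recurrent ketoacidosis as a reason for giving basal insulin before the infusion stops. It also lists a gap below 15 among the local criteria for moving to subcutaneous insulin, so readings near 12 around the transition are plausible. At stake is whether the reported result is the quantity the protocol names, and whether the choice between two readings of the outcome is left until the data are in hand.

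**Working it through.** The plan states no figure that depends on this point, so there is none to reproduce. The check compares the definition with the fields and then shows the consequence with assumed readings.

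**1. What each source measures.** Write T_def for the sum of all intervals with anion gap > 12 (Study aims), and T_form for the time of the first anion gap < 12 minus the start time (form). The two agree only if every reading before the first value < 12 is above 12 and no later reading is above 12.

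**2. Two constructed patients.** Assumed readings every 4 h from 0 to 24 h, each carried forward to the next draw:

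| Patient | Readings at 0, 4, 8, 12, 16, 20, 24 h | T_form | T_def | T_form − T_def |
|---|---|---|---|---|
| Gap reopens | 24, 18, 14, 11, 15, 13, 11 | 12 h | 5 intervals × 4 h = 20 h | −8 h |
| Gap sits at 12 | 24, 18, 12, 12, 11, 11, 10 | 16 h | 2 intervals × 4 h = 8 h | +8 h |

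The field can therefore be too short or too long for an individual patient.

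**3. Effect of reopening on an arm mean.** If a proportion p of patients reopen for h hours on average, the recorded mean falls short of the defined mean by p × h. The documents give neither p nor h, so both are assumed:

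| p | h = 4 h | h = 8 h |
|---|---|---|
| 5% | 0.2 h | 0.4 h |
| 10% | 0.4 h | 0.8 h |
| 20% | 0.8 h | 1.6 h |

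**4. Effect of reopening on the arm difference.** With the same h in both arms, the recorded difference (control minus glargine) falls short of the defined one by (p_control − p_glargine) × h.

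- 10% in both arms: (0.10 − 0.10) × 8 = 0 h.
- 20% control, 10% glargine: (0.20 − 0.10) × 8 = 0.8 h.
- 10% control, 20% glargine: (0.10 − 0.20) × 8 = −0.8 h.

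The sign depends wholly on which arm reopens more, which the documents do not say.

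**5. Scale.** The two-center randomized trial in the Background reports SDs of 6.4 and 6.8 h for time to anion gap closure. With the planned 66 per arm, the standard error of a difference in means would be √((6.4² + 6.8²)/66) = √(87.2/66) ≈ 1.15 h. An assumed shift of 0.8 h is about 0.7 of that. If the Wilcoxon branch is used, a change in a minority of patients need not act like a mean shift.

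**The case against.** The best defence is that only the wording in Study aims is loose. The Summary lists time to anion gap closure among the outcomes, the form's fields are there to calculate time to resolution, and the Statistical analysis plan treats outcome 3 as time to an endpoint. All three point to time to closure, which is a legitimate outcome. Time with a gap above 12 could also be read as the single initial episode. This stands as a likely account of what the team intends, and it is why rewording is an acceptable remedy. It does not remove the conflict: the definition as written says something else, and the form's threshold is wrong under either reading.

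A second defence is that staff can see serial values in the medical record. They can, but the plan does not list them for abstraction.

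A third is that cumulative time is itself fragile. One stray reading of 13 after closure would add a whole 4 h interval in the example above, and lab timing is outside the study's control, as Strengths and limitations concedes. This is fair and is counted below as a cost.

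A reader might also infer that the form biases the comparison against glargine, because the cited retrospective cohort says "There was no difference in transitional failure (early group: 6% vs late: 10"%). The documents do not support that. The cohort reports no difference (p = 0.717). The rates correspond to about 2 of 33 and 7 of 73 patients, and one more early failure would give 3/33 = 9%. Transitional failure is not defined in the protocol, so equating it with a gap above 12 would be a further assumption.

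**Conclusion.** The mismatch is real. The planned dataset cannot produce secondary outcome 3 as defined: it omits any time above 12 after a gap reopens, and it counts a reading of exactly 12 as elevated. In the constructed patients each error is 8 h, in opposite directions; those values are assumed.

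No size or direction can be given for the effect on the arm comparison, because the documents contain no reopening rate or duration and do not say how often a reading of exactly 12 occurs. Reopening that is equal in frequency and length would understate both means without shifting their difference. It would also go too far to infer that harm from recurrence would be hidden: recurrence that prolongs care can show in ICU or hospital stay, and adverse events are reported to the IRB.

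Severity is minor to moderate. One secondary outcome is affected, and the primary outcome is not.

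**What to change.** Choose one of two routes before outcome data are compared by arm.

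**Keep the duration.** Replace the first-value-below-12 field with all timed anion gap values from infusion start to a fixed horizon common to both arms, or to hospital discharge if earlier. Derive outcome 3 as total time above 12, with a written carry-forward rule that also covers the level at infusion start and the period after the last reading. Report time to the first value of 12 or less as supportive.

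**Adopt time to closure.** Reword outcome 3 in Study aims as time from infusion start to the first anion gap of 12 or less, correct the form threshold to match, and report the number of patients per arm whose gap later rises above 12. That count needs at least one added form item.

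Recording the timed values supports either route. Under Enrollment, staff already abstract the record through discharge, so the cost is a repeating REDCap field, a sentence or two in the analysis plan and some extra abstraction, with no new labs. The main drawback of the first route is that cumulative time is sensitive to reading noise and to lab timing, which the Statistical analysis plan warns may differ between arms.

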#### Population

##### Inclusion Criteria

- Presented to Regions Hospital ED for chief complaint of DKA, nausea, vomiting, abdominal pain, hyperglycemia, or similar
- Meets all below diagnostic criteria for DKA per the American Diabetes Association:
  - Arterial or venous pH  $\leq$  7.3
  - Serum Bicarbonate  $\leq$  18 mEq/L
  - Ketonuria or ketonemia
  - Anion Gap  $>$  10
  - Blood sugar  $>$  250 mg/dL
- Receiving IV insulin infusion
- It is feasible to provide insulin glargine within 2 hours (+/- 30 minutes) of IV infusion start
- Will be admitted to the ICU for DKA, or already admitted to the ICU for DKA
- Ability to provide informed consent

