### Enrollment

Once the patient is randomized, the CCRC intern will notify the ED pharmacist who will determine if patient is currently taking basal insulin and, if they are taking basal insulin prior to admission, will verify the home basal dosing. CCRC research staff will be notified of the dosing order from the randomization and will place the appropriate order. The patient will either receive 0.2 u/kg insulin glargine, current (prior to admission) basal insulin dose, or no additional treatment study protocol. CCRC staff will abstract the study data points from the patient’s EMR while the patient is in the Emergency Department, throughout their hospital stay, and again at the time of discharge. The ED pharmacist will time the insulin glargine dose to be administered optimally within two hours after initiation of the IV insulin infusion.

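### The data form cannot yield secondary outcome 2 (DKA recovery) as defined: bicarbonate is reversed, the glucose and anion-gap cut-offs differ, and only separate first crossings are kept

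*Combined protocol and SAP*

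**What the plan says.** Study aims, secondary outcome 2, asks about "faster recovery from DKA (defined as blood glucose < 200 and two of: Anion Gap" ≤12, bicarbonate ≥15 mEq/L, or pH >7.3. The Statistical analysis plan section fixes the timing: "the outcome measured is the time at which all of the necessary criteria are hit for the first time simultaneously". It gives the transience of some of these measures as the reason.

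The section on the variable list and data collection states that "The variables listed on the below data collection form will be incorporated into a secure REDCap database". The fields listed there for working out time to resolution include the first pH above 7.3, "Time of first blood glucose < 250 mg/dL", "Time of first anion gap < 12" and "Time of first serum bicarbonate < 15 mEq/L". The list has no field for glucose <200, for bicarbonate ≥15 or for simultaneous recovery, and no serial lab values.

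The Enrollment section says "CCRC staff will abstract the study data points from the" electronic record from the ED stay through discharge. The Data Confidentiality and Privacy section has electronic identifiers destroyed at close-out.

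**The concern.** The definition needs to know when several criteria are true at the same moment. The form keeps one time per lab, three of the four thresholds differ from the definition, and one of those points the wrong way. Nothing in the documents reconciles the two. An analyst holding only the database would have to invent a combining rule after the data are in. Some patients' recovery times would then be too early, some too late and some absent, and the plan gives no rule for a patient without a recovery time.

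Secondary outcome 3 (time with anion gap above 12) is affected less, through values of exactly 12 and gaps that reopen. ICU length of stay, the primary outcome, does not use these fields.

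**Working it through.** **1. Definition against form**

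| Lab | Definition (Study aims) | Form field | Match |
|---|---|---|---|
| Glucose, mg/dL | <200 | first <250 | no |
| Anion gap (AG) | ≤12 | first <12 | no, at exactly 12 |
| Bicarbonate, mEq/L | ≥15 | first <15 | no, reversed |
| pH | >7.3 | first >7.3 | yes |
| Timing | first moment held together | four separate first times | no |

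The glucose gap can matter. The Background section lists, among the hospital's transition criteria, glucose stable at 180–250 mg/dL for at least 4 hours, so a patient can spend hours between the two cut-offs.

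**2. What the bicarbonate field records**

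The Inclusion Criteria ("Meets all below diagnostic criteria for DKA per the American Diabetes Association") require bicarbonate ≤18. One draw cannot be both <15 and ≥15, so the field never holds the required time. A patient presenting below 15 is stamped at time 0. A patient presenting at 15–18 already meets ≥15 but gets a blank, or the time of a later fall. Bicarbonate is in two of the three pairs that satisfy two-of-three.

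**3. Formulas**

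The plan does not say how to combine the form's fields. I assume the two-of-three structure from Study aims. Without relapses:

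- Defined time = max(time glucose <200, second smallest of the times of AG ≤12, bicarbonate ≥15, pH >7.3).
- Form time = max(time glucose <250, second smallest of the times of AG <12, bicarbonate <15, pH >7.3).

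If presenting bicarbonate is <15, its form time is 0 and the form needs only AG or pH. If it is 15–18 and never lower, the form needs both AG and pH, while the definition needs only one.

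**4. Worked patients (assumed values; AG passes both cut-offs at once)**

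- Presenting bicarbonate 10; glucose <250 at 7 h and <200 at 10 h; AG at 9 h; bicarbonate ≥15 at 12 h; pH at 14 h. Defined: max(10, second of {9, 12, 14}) = max(10, 12) = 12 h. Form: max(7, second of {0, 9, 14}) = max(7, 9) = 9 h, **3 h early**.
- Presenting bicarbonate 16, never below 15; glucose at 6 h and 8 h; AG at 8 h; pH at 12 h. Defined: max(8, second of {0, 8, 12}) = 8 h. Form: max(6, second of {8, 12}) = 12 h, **4 h late**, or no time if pH is not rechecked.
- If AG and pH clear on the same panel after glucose, the two times agree.

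**5. Missing times and relapses (assumed draws every 4 h from time 0)**

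| Series | Glucose | AG | Bicarbonate | pH |
|---|---|---|---|---|
| A | 400, 260, 190, 180 | 20, 15, 12, 12 | 16, 17, 18, 19 | 7.28, 7.29, 7.32, 7.35 |
| B | 450, 190, 230, 240, 195 | 24, 19, 14, 12, 11 | 9, 12, 15, 16, 18 | 7.15, 7.22, 7.31, 7.33, 7.35 |

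Series A: defined 8 h. On the form only pH has a time, so recovery is **not calculable**. With all thresholds corrected it is 8 h.

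Series B: defined 16 h. Form: max(4, second of {0, 8, 16}) = 8 h. With all thresholds corrected but separate crossings kept: max(4, second of {8, 8, 12}) = **still 8 h**, because the glucose of 190 at 4 h did not last.

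Separate crossings and the 250 cut-off can only make recovery early. Late or missing times come from the reversed bicarbonate field, the strict AG cut-off, or both.

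**6. Illustrative simulation**

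No input below is in the documents. There were 20,000 patients per arm and scenario.

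- Glucose: median 500 (log SD 0.3), falling 60 mg/dL/h to 250, then 10, 25 or 50 mg/dL/h; hourly checks; noise SD 15.
- Bicarbonate: mean 9 or 12 (SD 4, cap 18), rising 0.6/h.
- AG: mean 24 (SD 5), falling 1.1/h.
- pH: mean 7.15 (SD 0.1, cap 7.30), rising 0.014/h.
- Noise SD 1, 1 and 0.015 for bicarbonate, AG and pH; panels every 2, 4 or 6 h.
- Correction 18% faster in the intervention arm.

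That is 3 × 3 × 2 = 18 scenarios.

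| Result | Range over scenarios |
|---|---|
| Form early | 25–67% |
| Form late | 8–31% |
| Form identical | 21–52% |
| Discordant if only the bicarbonate sign is corrected | 15–60% |
| Discordant if all thresholds are corrected, separate crossings kept | 0–5% |
| Mean between-arm difference, definition | 1.52–1.98 h |
| Mean between-arm difference, form | 1.43–1.72 h |
| Form difference as a share of the defined one, within scenario | 80–109% |

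Recoding the same assumptions from scratch gave 20–62% early, 9–32% late and the same 0–5%, so the ranges are approximate.

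**The case against.** The endpoint itself is clearly written, and the Statistical analysis plan section already requires simultaneity. No text tells anyone to combine first crossings as above; that rule is an assumption, so the percentages describe a calculation the plan never asks for. The bicarbonate sign is probably a typing error, since a fall below 15 makes no sense as a step to resolution. Missing times are not shown to be common: a rerun with pH on every panel gave 0%, and staff are to see that standard labs are completed. Once the thresholds are right, separate crossings matter little. Everything can be recovered from the medical record.

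Much of this stands. The percentages are secondary, and certainty attaches to the mismatch in the text, not to its frequency. But a clear definition does not help if the database lacks the values to apply it. Correcting only the sign leaves the glucose and anion-gap cut-offs and the simultaneity problem. Recovery from the record depends on acting before identifiers are destroyed.

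Two side points are matters of wording only. The planned adjustment for lab timing can fairly be read as referring to the draw schedule. The hypoglycemia field running from glargine to 24 hours after the infusion is limited to controls, which does not fit its role of capturing harm from the intervention; overall hypoglycemia is nevertheless recorded in both arms.

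**Conclusion.** The concern holds and should be fixed. As listed, the fields cannot give secondary outcome 2 as defined. That follows from the text alone. The bicarbonate field is wrong for every patient by construction; whether the derived recovery time is wrong depends on the order in which the labs clear. The worked cases show errors of 3 h early and 4 h late, a missing time, and a relapse that survives correction of the thresholds. Those cases assume the two-of-three rule is applied to the form's times.

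How many patients are affected cannot be known from the documents, which give no lab distributions. Under the assumed inputs, 48–79% had a time that differed from the definition (100 minus the 21–52% identical). The harm is mainly wrong patient-level times: the simulated effect estimate moved modestly, and no large bias is demonstrated. The primary outcome is unaffected.

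**What to change.** Reconcile the data form with Study aims and the Statistical analysis plan section.

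- Preferred: replace the first-crossing fields with time-stamped serial glucose, anion gap, bicarbonate and pH from the medical record. Derive recovery as the first time the plan's own criteria hold together, and time with anion gap above 12 from the same series.
- Smaller alternative, enough for outcome 2: correct the thresholds to the plan's definition and add one field for the time of first simultaneous recovery. Outcome 3 would still miss gaps that reopen.
- State that any lab-timing adjustment uses draw schedule or frequency, never the time to the lab that shows resolution. For outcomes 2 and 3 that time is essentially the outcome.
- Reconcile the control-only label on the hypoglycemia field with its stated role.

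The cost is a REDCap form correction, a few sentences in the plan, and some extra abstraction and programming. The labs are standard of care and staff already abstract the record through discharge, so no new tests are needed. For patients already enrolled, re-abstract before close-out.
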